HCQ has been shown to cause severe hypoglycemia including loss of consciousness that could be life threatening in patients treated with or without antidiabetic medications. Patients treated with HCQ should be warned about the risk of hypoglycemia and the associated clinical signs and symptoms. Patients presenting with clinical symptoms suggestive of hypoglycemia during treatment with HCQ should have their blood glucose checked and treatment reviewed as necessary.

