3.3.2 Hydroxychloroquine

Table 4 Guidelines for hydroxychloroquine-related toxicities

Adverse Event	1 st Occurrence	2 nd Occurrence
Hematology Grade 4 neutropenia lasting \geq 7 consecutive days Grade 4 thrombocytopenia \geq 7 consecutive days Grade \geq 3 neutropenia with fever (temperature \geq 38.5 °C)	Hold HCQ and trametinib. Continue weekly hematologic monitoring. Once AE resolves to \leq Grade 1, restart study drugs, with HCQ at next lower dose level.	Discontinue HCQ and trametinib
Skin and subcutaneous tissue disorders Grade \geq 3 rash, hand-foot skin reaction or photosensitivity lasting $>$ 7 consecutive days despite skin toxicity treatment	See Table 5	Discontinue HCQ and trametinib
Eye disorders Grade 2 retinal events lasting $>$ 14 consecutive days confirmed by ophthalmologic examination Grade \geq 3 retinal events confirmed by ophthalmologic examination	Hold HCQ and trametinib. Monitor until AE resolves to Grade \leq 1. Patients should be referred for ophthalmologic exam. Restart study drugs, with HCQ at next lower dose level.	Discontinue HCQ and trametinib
Gastrointestinal Grade \geq 3 nausea or vomiting lasting \geq 7 days despite optimal anti-emetic therapy	Hold HCQ and trametinib. Monitor until AE resolves to Grade \leq 1. Restart study drugs, with HCQ at next lower dose level.	Discontinue HCQ and trametinib
Grade \geq 3 diarrhea lasting \geq 7 days despite optimal anti-diarrhea treatment	See Table 6	Discontinue HCQ and trametinib
Hepato-biliary Grade \geq 3 total bilirubin felt to be not related to progression of disease Grade \geq 3 ALT (isolated increases in AST without concomitant increases in ALT will not be considered dose-limiting because of the non-specific nature of AST) Grade 4 alkaline phosphatase lasting \geq 7 consecutive days felt to be not related to progression of disease	Hold HCQ and trametinib. Monitor with weekly CMP until AE resolves to Grade \leq 1. Restart study drugs, with HCQ at next lower dose level.	Discontinue HCQ and trametinib
ECG QT Interval	Hold HCQ and trametinib. Monitor	Discontinue HCQ

Abbreviated Title: Trametinib and HCQ in BTC**Version Date: 04/06/2022**

Adverse Event	1 st Occurrence	2 nd Occurrence
QTcF interval \geq 501 ms on at least two separate ECGs	with ECG until AE resolves to Grade \leq 1. Restart study drugs, with HCQ at next lower dose level.	and trametinib

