Renal Serum creatinine \geq Grade 2	Check cystatin-C levels. If GFR calculated by cystatin C is \geq 30 mL/min/1.73 m ² , continue HCQ and trametinib. If GFR calculated by cystatin C is \leq 30 mL/min/1.73 m ² , hold HCQ and trametinib. Monitor with weekly CMP and cystatin C until AE resolves to \leq Grade 1. Restart study drugs, with HCQ at next lower dose level.	Check cystatin-C levels. If GFR calculated by cystatin C is \geq 30 mL/min/1.73 m ² , continue HCQ and trametinib. If GFR calculated by cystatin C is \leq 30 mL/min/1.73 m ² , discontinue HCQ and trametinib.* *2nd occurrence of elevated serum creatinine will only be determined if 1st occurrence included elevated cystatin C and dose reduction.
Hypoglycemia	Hold HCQ if Grade 2. Monitor AE until resolution to Grade \leq 1. Restart study drugs, with HCQ at next lower dose level. Hold HCQ if Grade 3. Monitor AE until resolution to Grade \leq 1. Restart study drugs HCQ at next lower dose level. Discontinue HCQ permanently if Grade 4	Discontinue HCQ and trametinib
Non-hematologic events Grade \geq 3, except for the exclusions noted below: • Grade 3 alopecia • < 5 days of Grade 3 fatigue • < 5 days of Grade 3 edema • Grade 3 laboratory abnormalities that are responsive to oral supplementation	Hold HCQ and trametinib. Monitor AE until resolution to Grade \leq 1. Restart study drugs, with HCQ at next lower dose level.	Discontinue HCQ and trametinib

Adverse Event	1 st Occurrence	2 nd Occurrence
or deemed by the investigator to be clinically insignificant		

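### Table 4 gives opposite instructions at a cystatin-C GFR of exactly 30, and its last row, not confined to other events, conflicts on a literal reading with several specific rows

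*Combined protocol and SAP*

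**What the plan says.** Table 4 lists HCQ-related adverse events by organ system, with one action for a first occurrence and another for a second.

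- **Renal row.** This applies to serum creatinine of Grade 2 or more and is decided by cystatin C. At 30 mL/min/1.73 m² or above the patient continues both drugs; at 30 or below both are held (first occurrence) or discontinued (second). The two limits stand on either side of the words "continue HCQ and trametinib. If GFR calculated by cystatin C is", and both cells use the same pair of signs. A footnote counts a second occurrence only if the first involved an abnormal cystatin C and a dose reduction.
- **Hypoglycemia row.** The Grade 4 instruction is "Discontinue HCQ permanently if Grade 4".
- **Gastrointestinal and skin rows.** Grade 3 or higher nausea or vomiting triggers action only after at least "7 days despite optimal anti-emetic therapy". Diarrhea has the same 7-day minimum, and rash must last more than 7 days.
- **Last row.** This covers non-hematologic events of Grade 3 or more. Its exclusions are Grade 3 alopecia, Grade 3 fatigue or edema of under 5 days, and Grade 3 laboratory values that respond to oral supplementation or that the investigator considers clinically insignificant. The first-occurrence action begins "Hold HCQ and trametinib. Monitor AE until resolution to Grade" 1 or lower, followed by a restart with HCQ one level down. A second occurrence stops both drugs.

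Nothing in section 3.3 says which row prevails when an event fits two.

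**The concern.** These are dosing instructions, and as written two clinicians could treat the same patient differently while both following the table. At a cystatin-C GFR of 30 on a second occurrence, one would continue both drugs and the other would stop both permanently.

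The last row names its own exclusions, and events with a dedicated row are not among them. The closing row of Table 6, for trametinib, is expressly labelled as covering other reactions, so the protocol uses that limit in one table and omits it in the other.

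The literal reading is not always the more cautious one. After Grade 4 hypoglycemia it allows HCQ to restart, although section 1.2.6.2 warns that "HCQ has been shown to cause severe hypoglycemia including loss of consciousness that could be life threatening". In the other direction, a second brief episode of Grade 3 vomiting would end both drugs, although the gastrointestinal row would not have acted on either episode. Section 3.6.1 refers back to section 3.3 for removal from therapy because of toxicity, so the choice of row can decide whether a patient stays on treatment.

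**Working it through.** This is a check of logic; the plan states no figure to reproduce.

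**Renal row.** Inputs are the two limits in Table 4: continue if GFR ≥ 30; hold (first) or discontinue (second) if GFR ≤ 30.

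| Cystatin-C GFR | Rule met |
|---|---|
| 29 and 29.9 | hold or discontinue only |
| 30 | continue, and also hold or discontinue |
| 30.1 and 31 | continue only |

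The overlap is the single value 30, in both occurrence columns. With the second limit changed to < 30, every value has one instruction and 30 means continue. That agrees with section 2.1.1, which admits patients with raised creatinine if clearance or eGFR is at least 30.

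**Last row against specific rows.** The HCQ dose one level down is the starting dose (section 3.1) less one step (section 3.3.1): 1,200 − 400 = 800 mg a day. The durations and the GFR of 45 below are illustrative values on the relevant side of each limit.

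| Event | Its own row | Last row, read literally |
|---|---|---|
| Grade 4 hypoglycemia, first | HCQ stopped for good | hold both; restart with HCQ at 800 mg a day |
| Grade ≥ 3 creatinine, cystatin-C GFR 45, first | continue both | hold both; HCQ lowered |
| The same, second | continue both | stop both |
| Grade 3 nausea or vomiting for 3 days, first | no action (limit ≥ 7 days) | hold both; HCQ lowered |
| Grade 3 diarrhea for 3 days, first | no action (limit ≥ 7 days) | hold both; HCQ lowered |
| Grade 3 rash for 5 days, first | no action (limit > 7 days) | hold both; HCQ lowered |
| A second brief episode of any of these four | no action | stop both |

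The laboratory exclusion does not reach Grade 4 hypoglycemia, because it covers Grade 3 only. It does not reach nausea, vomiting, diarrhea or rash, because they are not laboratory values. It can remove the creatinine conflict at Grade 3 if the investigator considers the value clinically insignificant, but not at Grade 4.

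**Where there is no conflict.** Grade 3 nausea for 8 days, Grade 3 ALT, a Grade 3 retinal event and QTcF of 501 ms or more receive the same first-occurrence action from both rows. Hematologic events and Grade 2 retinal events fall outside the last row.

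If the last row is confined to events without a row of their own, every conflict in the second table disappears.

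**The case against.** The strongest reply is that a general row placed after organ-specific rows is a conventional catch-all. On that reading the specific row governs; otherwise its grade and duration limits would have no purpose. This is almost certainly the intention. A reader might infer that the last row overrides the specific rows, but the documents do not support that: they rank neither above the other. What remains is that the rule has to be guessed, when Table 6 shows how easily it could be stated.

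A second reply is that Table 4 is headed as guidelines, and section 3.3 speaks of recommendations and gives the PI discretion. That softens the instructions. But the discretion concerns leaving the other drug unmodified when one drug alone is to blame; it does not say which row of Table 4 applies.

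A third reply is that Table 6 already withholds trametinib for Grade 3 skin toxicity and other Grade 3 reactions, with no duration limit. This stands and narrows the effect: for brief events attributed to trametinib, the open question is mainly what happens to HCQ and whether a second episode stops both drugs.

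A reader might also extend the list to Grade 3 alkaline phosphatase, isolated AST rises and Grade 3 hypoglycemia. These are weak examples. The alkaline phosphatase entry is silent at Grade 3 rather than contrary. The laboratory exclusion may cover both liver values, and section 6.1 records a laboratory value as an adverse event only if it is clinically consequential. The Grade 3 hypoglycemia text holds HCQ but then speaks of restarting the study drugs in the plural, so it does not clearly mean that trametinib continues.

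**Conclusion.** Both inconsistencies are present in the current text and should be corrected. The practical effect is low. The renal overlap is one boundary value and will seldom matter unless GFR is reported as a whole number. The last-row conflict affects practice only if someone applies the general row to an event that has its own.

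A reader might want to put a rate on this from Tables 2 and 3, but the documents do not support one. Table 2 describes trametinib without HCQ. Table 3 describes a triplet that included dabrafenib, gives no event durations, and does not list hypoglycemia. Table 4 applies only to toxicity attributed to HCQ. Table 3 shows no Grade 3 creatinine increase and the text reports no Grade 4 events, which is consistent with few affected patients but does not measure how many.

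Nor should anyone infer an effect on the 5-month progression-free endpoint, the two-stage design or the safety run-in. The run-in has its own DLT criteria in section 3.1.1, and no such effect is claimed.

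The conclusion assumes that the inequality signs are as printed. They are the same in both Renal cells, and strict signs appear elsewhere in the table.

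**What to change.** 1. In both Renal cells of Table 4, change the hold or discontinue limit from ≤ 30 to < 30 mL/min/1.73 m².
2. Relabel the last row *Other non-hematologic events Grade ≥ 3 not covered by a row above*, keeping its exclusions.
3. Add one sentence under the table: an event type named in a row follows that row, including its grade and duration limits.

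The cost is two inequality signs, one row label and one sentence, which can go into the next amendment. No test, visit or patient is added.

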3.3.3 Trametinib

Dose reductions for adverse reactions associated with trametinib are presented in **Table 5**

Table 5: Recommended Dose Reductions for Trametinib for Adverse Reactions

Action	Recommended Dose
First Dose Reduction	1.5 mg orally once daily
Second Dose Reduction	1 mg orally once daily
Subsequent Modification	Permanently discontinue if unable to tolerate trametinib 1 mg orally once daily

Dosage modifications for adverse reactions associated with trametinib are presented in **Table 6**.

Table 6 Recommended Dosage Modifications for Trametinib for Adverse Reactions

Severity of Adverse Reaction ^a	Dosage Modification for Trametinib ^b
Venous Thromboembolism	
Uncomplicated deep venous thrombosis (DVT) or pulmonary embolism (PE)	Withhold trametinib for up to 3 weeks. 
• If improved to Grade 0-1, resume trametinib at lower dose.• If not improved, permanently discontinue trametinib.
Life threatening PE	
Cardiomyopathy	Permanently discontinue trametinib.
Asymptomatic, absolute decrease in left ventricular ejection fraction (LVEF) of 10% or greater from baseline and is below institutional lower limit of normal (LLN) from pretreatment value	Withhold trametinib for up to 4 weeks. 
• If improved to normal LVEF value, resume trametinib at lower dose.• If not improved to normal LVEF value, permanently discontinue

Severity of Adverse Reaction^a	Dosage Modification for Trametinib ^b
	trametinib.
Symptomatic cardiomyopathy Absolute decrease in LVEF of greater than 20% from baseline that is below LLN	Permanently discontinue trametinib.
Ocular Toxicities	
Retinal pigment epithelial detachments (RPED)	Withhold trametinib for up to 3 weeks. 
• If improved, resume trametinib at same or lower dose.• If not improved, permanently discontinue trametinib or resume trametinib at lower dose.
Retinal vein occlusion (RVO)	Permanently discontinue trametinib.
Pulmonary	
Interstitial lung disease (ILD)/pneumonitis	Permanently discontinue trametinib.
Febrile Reactions	
Fever higher than 104°F Fever complicated by rigors, hypotension, dehydration, or renal failure	Withhold trametinib until fever resolves, then resume trametinib at same or lower dose.
Skin Toxicities	
Intolerable Grade 2 Grade 3 or 4	Withhold trametinib for up to 3 weeks. 
• If improved, resume trametinib at lower dose.• If not improved, permanently discontinue.
Severe cutaneous adverse reactions (SCARs)	Permanently discontinue trametinib.
Other Adverse Reactions, including Hemorrhage	

Severity of Adverse Reaction^a	Dosage Modification for Trametinib ^b
Intolerable Grade 2	Withhold trametinib
Any Grade 3	
• If improved to Grade 0-1, resume at lower dose.• If not improved, permanently discontinue.
First occurrence of any Grade 4	
• Withhold trametinib until improves to Grade 0-1, then resume at lower dose. 
Or
 
• Permanently discontinue trametinib.
Recurrent Grade 4	Permanently discontinue trametinib.

^a National Cancer Institute Common Terminology Criteria for Adverse Events (NCI CTCAE) version 5.0.

^b See **Table 5** for recommended dose reductions of trametinib.

3.4 Study Calendar

	Screening	Baseline¹	Day 1 of every cycle¹	Weekly²	28 Days Safety FU^{13, 15}	Long Term FU^{14,15}
Trametinib ³			X	X		
Hydroxychloroquine ⁴			X	X		
Medical History	X					
Height	X					
Histologic confirmation of disease	X					
KRAS mutational status	X					
Ophthalmology consult ⁵	X		X			
Cardiology evaluations ⁶	X		X			
24-hour urine (if indicated)	X					
Infectious diseases testing ⁷	X					
Physical exam, weight and ECOG	X		X		X	X
Vital Signs	X		X		X	
CBC w/differential, Platelets	X		X	X	X	X
Biochemical profile ⁸	X		X	X	X	X
CK			X			
Urinalysis		X				
Pregnancy test ⁹	X		X			
Thyroid tests TSH, T3, T4			X		X	
Uric acid, amylase and lipase			X	X	X	
PT, INR, PTT, fibrinogen			X	X	X	
Tumor marker CEA, AFP, CA19-9			X		X	
Baseline signs and symptoms		X				
Concomitant medications	X	X	X			
Adverse event evaluation			X		X	

Abbreviated Title: Trametinib and HCQ in BTC**Version Date: 04/06/2022**

	Screening	Baseline¹	Day 1 of every cycle¹	Weekly²	28 Days Safety FU^{13, 15}	Long Term FU^{14,15}
Radiologic Evaluation ¹⁰	X	X	X			X
Tumor biopsy ¹¹		X		X		
Research blood for whole exome/panel		X				
Research blood for Immune monitoring ¹²			X			
Research blood for serum p62 ¹²			X			
Phone call or e-mail for survival every 6 month						X

¹ Baseline and C1D1 evaluations do not need to be repeated if performed on screening or baseline in designated time frame. Cycle=28+/-3 days. All evaluations will be done within 3 days before Day 1 of every cycle. Screening evaluations will be repeated if treatment does not start within 28 days after screening.

² Weekly until first restaging, after that every two weeks during treatment. Outside labs are acceptable.

³ 2 mg of trametinib daily every day of every cycle.

⁴ 600 mg of HCQ PO twice daily every day of every cycle.

⁵ A standard ophthalmologic exam must be completed at screening, C2D1, and every 3 cycles thereafter (i.e. C5D1, C8D1, etc.) and as clinically indicated to assess for retinopathies. The screening ophthalmologic exam should include: best corrected distance visual acuity (BCVA), an automated threshold visual field (VF) of the central 10 degrees (with retesting if an abnormality is noted), and spectral domain ocular coherence tomography (SD-OCT). Outside evaluations are acceptable.

⁶ EKG must be performed at screening and on Day 1 of every cycle. Echocardiogram must be completed at screening, C2D1, and every 3 cycles thereafter (i.e. C5D1, C8D1, etc.) and as clinically indicated. Troponin I test and cardiology consult only if clinically indicated.

⁷ HIV, Hepatitis B and C serology. If screening serology results indicate potential HBV or HCV infection, viral load will be tested before starting investigational agents. TB testing will be performed only if clinically indicated.

⁸ Biochemical Profile: electrolytes, BUN, creatinine, AST, ALT, total and direct bilirubin, calcium, phosphorus, albumin, magnesium.

⁹ Pregnancy test for female participants of childbearing potential (serum or urine; if urine is positive it must be confirmed with serum test

Abbreviated Title: Trametinib and HCQ in BTC

Version Date: 04/06/2022

¹⁰ CT scan of chest, abdomen and pelvis (or MRI of chest, abdomen and pelvis if clinically indicated) every 8 (+/-1) weeks after start of study therapy. If patient taken off treatment for reason other than progression, CT scans will continue until progression or 5 months have passed since the start of study therapy whatever comes earlier. MRI of brain can be done at screening if clinically indicated.

¹¹ Mandatory tumor biopsies will be performed at baseline and any day during week 3 of cycle 2. If patient disease progresses before this, post-treatment biopsy might be performed per PI discretion at the time of progression.

¹² On Day 1 of cycles 1-4, then every 12 weeks until PD

¹³ +/- 1 week

¹⁴ After Safety Follow Up visit, subjects will be followed for adverse events by phone call or e-mail at 60 (+/- 14 days) and 90 (+/- 14 days) days. After that every 6 (\pm 1) months by phone call or e-mail for survival. If patient is taken off treatment for reason other than disease progression before 5 months have passed since the start of study therapy, we will continue to invite patient every 8 (+/-1) weeks for imaging studies until disease progression or 5 months have passed since the start of study therapy whatever comes earlier. Outside scans are acceptable.

¹⁵ If patients are not willing to come to the NIH Clinical Center, they may be followed by phone call or e-mail.

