3 STUDY IMPLEMENTATION

3.1 Study Design

The proposed study is an open label, single-arm phase II study of trametinib in combination with hydroxychloroquine (HCQ) in BTC patients (**Schema 1**).

Initially, 6 patients will be enrolled into safety run-in portion of the trial (section **3.1.2**). If safe, we will continue enrollment as planned, if not, we will submit next amendment with new study design.

Initially, 10 patients will be enrolled and evaluated for progression. Enrollment will be temporarily halted after the 10th patient has been accrued, unless we know that 3 patients have passed the 5-month point without progression. If 3 or more of the first 10 patients enrolled have not progressed at the 5-month evaluation, then accrual will continue until a total of 17 patients have been entered. If, among the first 10 patients accrued, 0 to 2 are able to be progression-free at the 5-month evaluation, then no further patients will be enrolled after such a determination has been made. If 6 or more of the total cohort of 17 patients have been found to be progression-free at 5 months, then this will indicate an adequate progression free probability to justify further consideration of trametinib in combination with hydroxychloroquine in this population of patients. On the other hand, if 3 to 5 of 17 are progression-free at 5 months, this will be considered insufficient.

Treatment with trametinib and HCQ will be delivered in cycles consisting of 4 weeks (+/- 3 days) and start on cycle 1 day 1.

Both drugs will be given orally on daily basis: trametinib (2 mg once a day) and HCQ (600 mg twice a day – 1,200 mg total dose).

[figure not shown]
Treatment with study drugs will continue until off treatment criteria are met (see section **3.6.1**).

If one of the study drugs is permanently discontinued because of toxicity, per PI discretion the patient may continue the other study drug. It is unclear in terms of the attitude and duration of antitumor efficacy with this drug combination in BTC. If patient's disease is controlled with the combination but the treatment is held because of AEs from one of the agents, we think it would be beneficial for participants to continue the other agent and continue monitoring the disease progress accordingly.

Patients will be monitored every 8 (+/- 1) weeks with imaging studies.

Patients will be evaluated for toxicity and malignancy per Study Calendar **3.4**.

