3.1.1 Dose Limiting Toxicity (DLT) (Safety Run-In only)

The DLT period is one cycle, 28 days, starting on Day 1 of cycle 1 after study drugs administration.

The following events will be considered DLTs (CTCAE v5.0) if attributable (definite, probable, possible) to the combination of study drugs:

Toxicity Category	DLT Criteria (grade per CTCAE 5.0)
Hematology	Grade ≥ 4 neutropenia lasting ≥ 7 consecutive days and/or not resolving within 48 hours to a grade 2 or less toxicity after correctible treatment
	Grade ≥ 4 thrombocytopenia lasting ≥ 7 consecutive days and/or not resolving within 48 hours to a grade 2 or less toxicity after correctible treatment
	Grade ≥ 3 neutropenia with fever (temperature ≥ 38.5 °C), not correctible within 48 hours to a grade 2 or less toxicity
Skin and subcutaneous tissue disorders	Grade ≥ 3 rash, hand-foot skin reaction or photosensitivity lasting > 7 consecutive days and/or not resolving within 48 hours to a grade 2 or less toxicity after correctible treatment
Eye disorders	Grade ≥ 2 retinal events lasting > 14 consecutive days confirmed by ophthalmologic examination
	Grade ≥ 3 retinal events confirmed by ophthalmologic examination, not correctible within 48 hours to a grade 2 or less toxicity
Gastrointestinal	Grade ≥ 3 nausea or vomiting lasting ≥ 7 days and/or not resolving within 48 hours to a grade 2 or less toxicity after correctible treatment
	Grade ≥ 3 diarrhea lasting ≥ 7 days and/or not resolving within 48 hours to a grade 2 or less toxicity after correctible treatment

	Grade \geq 3 total bilirubin not related to progression of disease, not correctible within 48 hours to a grade 2 or less toxicity
	Grade \geq 3 AST or ALT (isolated increases in AST without concomitant increases in ALT will not be considered DLT because of the non-specific nature of AST), not correctible within 48 hours to a grade 2 or less toxicity.
Hepatic	Patients with liver metastases will require AST or ALT levels 10 x ULN (isolated increases in AST without concomitant increases in ALT will not be considered DLT because of the nonspecific nature of AST).
	Grade \geq 4 alkaline phosphatase lasting \geq 7 consecutive days and/or not resolving within 48 hours to a grade 2 or less toxicity after correctible treatment
ECG QT Interval	QTcF interval \geq 501 ms on at least two separate ECGs, not correctible within 48 hours to a grade 2 or less toxicity

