Renal	Serum creatinine $> 2 \times$ ULN, not correctible within 48 hours to a grade 2 or less toxicity
Exceptions to DLT criteria	Grade 3 alopecia
	< 5 days of Grade 3 fatigue
	< 5 days of Grade 3 edema
	Grade \leq 4 lymphopenia
	Grade \leq 4 laboratory abnormalities that are responsive to oral supplementation or deemed by the investigator to be clinically insignificant.

3.1.2 Safety Run-In:

Six patients will be enrolled in a staggered fashion with at least 7 days minimum between each patient enrolled. If < 2 patients experience DLTs, as defined in section [3.1.1](#), we will proceed to the following portion of the trial. If ≥ 2 patients experience DLT, we will stop enrollment and will submit next amendment with new study design.

Subjects who do not start or do not complete the DLT observation period for reasons other than a DLT will be replaced and not included in the evaluation.

In case of DLT, DLT will be documented and patient, per PI discretion, may continue study treatment if toxicity could be managed by interruption of study treatment or dose reductions (See Section [3.3](#)).

Patient will be eligible for the DLT evaluation if at least ≥ 80 percent of trametinib and HCQ scheduled doses were taken within the DLT period.

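### Safety run-in: no clinical adverse event evaluation is scheduled between C1D1 and C2D1, and the next patient's first dose does not depend on a review of earlier patients

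*Combined protocol and SAP*

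**What the plan says.** Section 3.1 refers the schedule of toxicity assessment to the calendar: "Patients will be evaluated for toxicity and malignancy per Study Calendar". Neither 3.1.1 nor 3.1.2 adds a visit or call for the run-in.

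In the calendar (3.4), the row "Adverse event evaluation" has marks under Day 1 of every cycle and the 28-day safety follow-up only. Physical exam with ECOG and vital signs are also unmarked in the Weekly column. Footnote 6 puts the EKG at screening and on Day 1 of each cycle. Footnote 5 puts the on-treatment eye exam at C2D1 and every three cycles after, "and as clinically indicated to assess for retinopathies". In cycle 1 the Weekly column holds dosing and laboratory tests (the biopsy marked there falls in cycle 2). Footnote 2 defines the column: "Weekly until first restaging, after that every two weeks during treatment. Outside labs are acceptable". Footnote 1 sets the cycle at 28 +/- 3 days and adds: "All evaluations will be done within 3 days before Day 1 of every cycle".

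Section 3.1.1 sets a 28-day DLT window. Several criteria are clinical, for example grade 3 or higher "rash, hand-foot skin reaction or photosensitivity lasting" more than 7 days, together with nausea or vomiting, diarrhea, retinal events and QTcF. Section 3.1.2 sets the stagger: "Six patients will be enrolled in a staggered fashion with at least 7 days minimum between each patient enrolled". It proceeds with fewer than 2 DLTs in six patients and stops otherwise. It names no review between patients.

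Elsewhere, 7.3 has the team meet weekly to discuss each patient, and 6.1 documents AEs from C1D1. The diary (Appendix C) has a column for side effects. It is brought to clinic visits and, under 14.1.2, returned after each cycle.

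**The concern.** A stagger protects later patients only to the extent that something is learned from earlier ones before the next is dosed. For laboratory toxicity the plan provides this through the weekly bloods. For skin and gastrointestinal toxicity, visual symptoms and QTc, nothing is scheduled until C2D1, so a 7-day gap may pass without anyone having been asked about them.

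Timing and definition both matter. Section 1.2.5.2 gives a median onset of 15 days for trametinib skin toxicity (any grade, so not a DLT rate), which falls inside the interval with no scheduled clinical check. Several DLT criteria turn on duration (7 or 14 days) or on resolution within 48 hours. Those are easier to apply with dated grades from within the cycle than with recall at its end.

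At stake is the exposure of the second and later run-in patients to a combination for which 1.2.6.3 says no toxicity data were available, apart from a triplet study that also gave dabrafenib. Prior experience moderates the risk: 1.2.4.2 describes grade 1-2 toxicity as typical in 10 patients at these doses, and the triplet study reported no grade 4 events. That study did report grade 3 rash in 12%, grade 3 dehydration in 8% and grade 3 QTc prolongation in 4%.

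**Working it through.** The plan gives no figure of its own on this point, so the check reads the calendar against the stagger.

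**Inputs.** Cycle 28 +/- 3 days, with Day 1 evaluations up to 3 days early (3.4, footnote 1). DLT window 28 days (3.1.1). Minimum 7 days between enrolments, six patients (3.1.2). Accrual up to 10 a year (10.2). Assumption: first dose on the day of enrolment.

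**1. When the first on-treatment AE evaluation falls.** C2D1 = Day 29 +/- 3 = Day 26 to 32. Allowing 3 days early, the range is Day 23 (26 - 3) to Day 32, which is 22 to 31 days after first dose.

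**2. What the weekly labs reach.**

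| DLT group (3.1.1) | Scheduled check between C1D1 and C2D1 |
|---|---|
| Neutropenia, thrombocytopenia | Weekly CBC |
| Bilirubin, AST/ALT, creatinine | Weekly biochemistry |
| Rash, hand-foot reaction, photosensitivity | None |
| Nausea/vomiting, diarrhea | None directly; electrolytes and creatinine bear on severe cases |
| Retinal events | None; eye exam at C2D1 |
| QTcF | None; EKG at C2D1 |

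**3. Minimum spacing.** Starts fall on Days 1, 8, 15, 22, 29 and 36. Patient 1's first scheduled evaluation is no earlier than Day 23, so patients 2, 3 and 4 (Days 8, 15, 22) start before it. If it falls as late as Day 32, patient 5 (Day 29) does too. Scheduled post-dose AE evaluations available before patients 2, 3 and 4: 0, 0 and 0. Weekly lab sets are available over the same period.

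**4. Expected accrual.** At 10 a year the mean gap is 365/10 = 36.5 days, longer than the latest evaluation (31 days after dose). As an illustration, assume random arrivals with a 7-day floor: gap = 7 days plus an exponential remainder of mean 36.5 - 7 = 29.5 days.

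- A start precedes the previous patient's first evaluation with probability 1 - exp(-(22 - 7)/29.5) = 0.40 to 1 - exp(-(31 - 7)/29.5) = 0.56. Over five later starts that is 2.0 to 2.8.
- At 5 a year (mean 73, remainder 66): 1 - exp(-15/66) = 0.20 to 1 - exp(-24/66) = 0.30, or 1.0 to 1.5 of five.
- The pattern in step 3, with all of patients 2 to 4 starting before patient 1's evaluation, is rare at 10 a year. Three gaps must total under 31 days, so three remainders must total under 31 - 21 = 10 days. With x = 10/29.5 = 0.339, the probability is 1 - exp(-x)(1 + x + x²/2) = 0.005. That is the upper figure, with the evaluation at its latest.

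**5. What weekly checks would add at minimum spacing.** Checks on each patient's Days 8, 15 and 22.

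| Next start | Checks on earlier days only | Including same-day checks |
|---|---|---|
| Patient 2 (Day 8) | 0 | 1 |
| Patient 3 (Day 15) | 1 | 2 + 1 = 3 |
| Patient 4 (Day 22) | 2 + 1 = 3 | 3 + 2 + 1 = 6 |

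The right-hand column applies only if the same-day check is done and reviewed before dosing.

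**6. Workload.** 3 contacts x 6 patients = 18. On Day 29, patients 2, 3 and 4 are on Days 22, 15 and 8, so a pre-dose review covers at most three patients still in the window.

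**The case against.** The strongest reply is that the plan already has the parts it needs. The team meets every week and discusses each patient, which matches the 7-day stagger. AEs are documented from C1D1, patients keep a side-effect diary, and section 12.4.1.9 promises frequent monitoring. Visual complaints prompt an eye evaluation (1.2.5.2). Patients with severe rash, vomiting or diarrhea are likely to report it unprompted. This is also a fixed-dose run-in at doses used before, not an escalation.

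Much of this stands, and it is why the point is small. It does not close the gap. The meeting can discuss only what has reached it, and no clinical input on these toxicities is scheduled before C2D1. Section 6.1 says what is recorded, not when patients are asked. The diary comes back with the cycle, and frequent monitoring is given no schedule beyond the calendar.

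Two limits on the remedy also stand. Calls mainly catch skin and gastrointestinal toxicity and visual symptoms; they cannot see a silent QTc change or confirm a retinal event. And at minimum spacing patient 2 gains nothing unless the Day 8 check is reviewed the same day or the start moves.

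A reader might also infer that first doses can bunch together because the stagger applies to enrolment while footnote 1 says "Screening evaluations will be repeated if treatment does not start within 28 days after screening". That limit runs from screening to treatment, not from enrolment, so it demonstrates no gap between enrolment and dosing. All that can be said is that 3.1.2 does not itself set the spacing of first doses.

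**Conclusion.** The point holds as a cheap improvement, with medium confidence. Between C1D1 and C2D1 the calendar schedules no clinical AE evaluation, the weekly labs do not reach five kinds of DLT (rash, nausea/vomiting, diarrhea, retinal, QTcF), and 3.1.2 sets no review before the next first dose.

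Its size depends on spacing. At the permitted minimum, three of the five later patients start before patient 1's first scheduled evaluation. At up to 10 a year that full pattern is unlikely. Overlap with the immediately preceding patient would affect roughly 2.0 to 2.8 of five starts, and 1.0 to 1.5 at half that rate. These figures assume random arrivals and dosing at enrolment, which the documents do not state.

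A reader might infer that run-in patients go unmonitored for a month, or that the run-in is unsafe. The documents do not support either: blood, liver and kidney DLTs are covered weekly, AEs are recorded throughout, exams can be done when indicated, and no excess harm is quantified. Nor should the remedy be credited with 1, 3 and 6 prior checks without qualification; on earlier-day checks alone the gain is 0, 1 and 3.

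**What to change.** Two edits.

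- In 3.4, mark the adverse event row in the Weekly column for cycle 1 of the run-in, by phone or visit on the existing lab day (about Days 8, 15 and 22). Footnote 14 already accepts phone or e-mail contact for AEs in follow-up.
- In 3.1.2, state that before each next first dose the investigator reviews the latest weekly AE check and labs of every run-in patient still in the 28-day DLT window, without having to wait for the 7.3 meeting.

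The cost is about 18 contacts by existing staff and no new procedure. A start may slip by some days if a check is late, or by up to about a week if the site lets the review wait for the weekly meeting. Detection of silent QTc change and confirmation of retinal events stay with the EKG and the eye examination.
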